Sponsor Representative	[name] Laboratory of Medical Research and Consumer Involvement Department of Public Health IRCCS Istituto di Ricerche Farmacologiche “Mario Negri”
Background and rationale	Breast cancer is the most common cancer in women. In Italy, women are invited to a population-based mammography screening programme for the first time at the age of 45 or 50 years. Results from randomised controlled trials, observational studies, and systematic reviews continuously fuel the debate on the balance on benefits (reducing breast cancer mortality) and harms (overdiagnosis, overtreatment) of mammography screening. Physicians, policy makers, as well as laypeople or patient associations agree on the need to inform women about the potential benefits and harms in order to allow an aware decision process. Decision aids are an effective way to support lay people in their decisions about health.
Objectives Primary	To assess the effect of an interactive web decision aid on informed choice – measured through knowledge, attitudes and intentions concerning breast cancer screening – comparing the decision aid with a standard information provided via web (web brochure).
Secondary	
• To compare the participation rate in breast cancer screening between intervention (web decision aid) and control group (web brochure).• To compare the satisfaction between the intervention (web decision aid) and the control group (web brochure) on information in terms of length, quantity, clarity, balance, helpfulness in making decision and women willingness to recommend it to other women.• To measure the time spent on web pages between the intervention (web decision aid) and the control group (web brochure). Only for the intervention group, to measure number of pages visited, frequency of access, level of information and level of detail reached on the main topics.

	
 • To compare the decisional conflict process between the intervention and the control group.
Study design	Multi-centre, randomised, controlled study
Number of centers	More than 3
Number of patients	8160 women will be invited in order to reach 816 patients evaluable for primary endpoint.
Target population	The women aged 45-69 or 50-69 years new invited to the regional screening programmes of the participant centers .
Inclusion criteria	
 • Women aged 45-69, according to the target age of the screening centres involved; • New invited women in mammography screening programme.
Exclusion criteria	None
Assessment schedule	Baseline questionnaire prior to randomization Follow-up questionnaire 7-10 days after the randomization
Endpoints	
Primary
 
Informed choice, based on the available literature, will be measured according to the three-dimensional framework which covers knowledge, attitude and intention. Knowledge will be measured using a questionnaire structured in thirteen questions with multiple choice answers, with two to four options. Ten questions will be qualitative and 3 will be numerical. A score of 8 out of 13 (about 60%) or higher would be considered “adequate knowledge”.
 
Attitude will be measured through a scale consisting of six items with five response options from 1 to 5, with a total score from 6 to 30. For informed choice, we set the threshold for a positive attitude at 24 and consequently the score <24 point a negative attitude.
 
Intention to be screened will be measured using one item with five responses: Definitely will, Likely to, Unsure, Not likely to, Definitely will not. For informed choice, we classified “definitely will” and “likely to” as positive intentions.
 
A woman will be judged to have made an informed choice if she has adequate knowledge and her attitudes and intentions are consistent (both positive or both negative) in the follow-up questionnaire.

Secondary	
Participation rate to the breast cancer screening programme will be assessed as a percentage of women who actually participate, both in intervention and in the control group.
 
Satisfaction with the given information will be measured using 8 items with three points scale.
 
The time spent on the pages on the web decision aid and in the web brochure will be assessed through Pickwick software. Only for the web decision aid, through the same software, the number of pages visited, the frequency of access and level of detail reached will be calculated.
 
Decisional conflict will be assessed using the validated and widely used Decisional Conflict Scale-SURE version, consisted in four-item scale.

Planned study period	15 months (september 2017-december 2018)

LIST OF ABBREVIATIONS AND DEFINITION OF TERMS

e-CRF	Electronic Case Report Form
GCP	Good Clinical Practice
GISMA	Italian Group for Mammography Screening
ICH	International Conference of Harmonisation
IEC	Independent Ethics Committee
NHS	National Health Service
ONS	National Centre for Screening Monitoring
RCT	Randomised controlled trial
UK	United Kingdom
US	United States
WMA	World Medical Association

1. BACKGROUND

Breast cancer is the most common cancer in women. Population ageing, impact of early diagnosis and new treatments have changed the epidemiology of the disease in last decades. According with the annual report AIOM/AIRTUM the esteem of the number of new diagnosis of breast cancer in 2016 is 50.000 (1).

Since the end of the eighties, most European western countries have implemented national or regional population-based breast cancer screening programmes. Service screening programmes invite women, mostly in the age 50-69 years, to high quality mammography screening every 2 years according with European Guidelines (2). A recent survey (3) estimated about 26 millions of women received invitation in Europe.

1.1 Evidence and controversy

Screening mammography was first shown to be effective in reducing breast cancer mortality by the Health Insurance Plan randomised controlled trial (RCT) in US in the sixties (4). During the seventies, other 8 RCTs contributed evidence on breast cancer screening efficacy for reducing breast cancer mortality. Wald et al. in 1993 reported an estimate of 20% mortality reduction, based on the RCTs available (5). On that basis, the UK National Health Service (NHS) promoted service screening with invitation of the target population evaluating benefits, harms and costs. Over the nineties, several European countries implemented service screening as public health programmes. In 2003, the European Council Recommendation promoted the implementation of screening programmes in Europe, for breast, bowel and cervical cancer.

Evidence-based demonstration of the breast cancer mortality reduction related to screening mammography is the object of longstanding controversy. Since the beginning, opinions were clashing about the efficacy in younger women. Screening in premenopausal women was less sensitive and evidence of efficacy not shown in RCTs.

In Europe, service screening was restricted to women after 50 years of age, even if some programmes include also women aged 45-50 years. In USA, the National Cancer Institute-NIH Consensus Conference confirmed how sensitive the question of mammography screening in younger women was (6). The UK Age trial, enrolling women at 40-41 years of age, reported positive results, whereas not statistically significant (7).

Over the nineties, the debate continued especially about the study design and potential biases of the Canadian trial with an hot debate (8). In 2001, the publication of Nordic Cochrane systematic review (9), which classified the RCTs on the basis of their quality, and excluded some trials,

demonstrated the absence of efficacy of mammography screening, and re-ignited the controversy in US and Europe. In 2012, the NHS-UK set up an Independent Panel aimed to review the evidence and highlighted the importance of the continuation of the service-screening programme, but asked for changes in the communication and the information about benefits and harms, especially in terms of overdiagnosis of breast cancer (10). In 2012, the Euroscreen working group reviewed the outcome research from the European countries and published a supplement of the Journal of Medical Screening with an estimate of a first European balance sheet of the benefits and harms of service screening (overdiagnosis, overtreatment, and false positive results)(11). Several systematic reviews of the evidence have been published, including the Nordic Cochrane systematic review updates, with substantially different conclusions and data interpretation(12).

The evaluation of screening outcomes and communication to both stakeholders and women was a central issue. Promotion of informed decision making about breast cancer screening balance of benefits and harms was considered responsibility of the public health system.

1.2 Information and Communication

Some studies have shown that women are not aware of the value of mammography screening, thus confounding early diagnosis with prevention (13, 14). Other studies have shown that both leaflets and websites do not provide balanced information to women, most of them highlighting more the benefits than the risks, such as overdiagnosis and overtreatment (15-17). Qualitative studies have discussed how to balance the evidence-based information to enable women to participate in health care decision (18).

Different models of information have been suggested, as well formally tested in RCTs (19, 20). Among these, decision aids are an effective way to assist women to make a decision about mammography screening. According to a recent Cochrane review (21) and a clinical trial (22) on breast cancer screening, decision aid improves patients' knowledge, reduce decisional conflict clarifying their values, and could encourage women to take a more active role in decision making without anxiety.

1.3 Information and Media

Media are not always able to ensure a correct and adequate information about benefits and limits of mammography screening. The British Medical Journal published an update of the Canadian study on mammography screening carried out in early '80s (8). Media coverage was focused on the limits of the screening described in the study, without mentioning the multifaceted discussion on

screening (23, 24). Owing to the necessity to highlight the latest news, media leans toward a "last reading" of a complex health theme as a rule, releasing contradictory and often inconsistent information. The social media can offer a different approach with an abundance of voices reflecting different points of view.

1.4 Information and scientific societies

In Italy, the Italian Group for Mammography Screening (GISMA) and the National Centre for Screening Monitoring (ONS) addressed many efforts in promoting a high quality level communication for women invited by a population-based breast cancer screening programme. A Working Group on Communication has been created with the involvement of all screening professionals who have developed experience and knowledge on this issue over the years, with a multidisciplinary approach. The main objective of this group is to increase the awareness and knowledge on mammography screening among women, health operators, advocacy groups, and stakeholders. How to build a comprehensive and effective communication strategy, in order to obtain an informed participation, has been extensively debated within this group as long as what kind of experimental communication strategies with a multilevel and multi-professional approach should be set up in a screening context (25). However, the several GISMA screening centers adopted different leaflets to invite the women to participate in the breast cancer screening programme.

The debate concerning mammography screening is still lively although most of the stakeholders - physicians, policy makers, as well as lay people or patients' associations - agree on the need to inform women properly and consider this an ethical obligation. There is in fact an agreement in public health community about the relevance of communication of the outcomes in mammography screening. The uncertainties about the estimates, especially of potential harms deriving from mammography screening, should be explicit in screening communication tools. Cancer screenings share with other health sectors the communication issue. Communicating by considering patients' needs and willingness is a widespread problem in biomedicine today, and in several countries there are efforts to move for a better communication, taking into account the level of information requested by each woman. Furthermore, the current debate on mammography screening adds a new challenge: how disagreement among scientists should be managed, and how public health institutions and scientists should cope with communication in presence of divergences and conflicts on data.

2. STUDY RATIONAL

In consideration of the above mentioned issues, who can decide the amount and kind of information that should be delivered to women invited to mammography screening? In this project the distinction between the decision-making process at population/community level and at individual level has been considered. In the population framework, the decision making process should be based only on a rational and honest balance between benefits and harms, and the final responsibility for the choice between controversial estimates and interpretations belongs to the screening proponents, after considering the stakeholders' point of view. On the other hand, at individual level, the decision belongs to screened participants, that decide also what and how much information is essential for them to reach a completely informed decision. The individual final choice can diverge from a pure rational process and should be based on values and preferences, not only on a simple balance sheet which, for its intrinsic characteristics, cannot be applied at individual level. This distinction is based on the evidence that individual decision making process is not wholly consequence of a rational understanding of facts and figures, but can also be related to other individual-related factors as values, emotions, preferences, confidence, trust and so on. All these elements greatly vary from person to person, and also over time. The “rational agent” model of decision making is today widely under revision by the cognitive science approach, and also by the results achieved in the game theory and economics fields. The screening promoters have the duty to provide all the relevant information for an informed choice, including those related to the uncertainty of the estimates and the scientific controversy. Furthermore, it is up to the screening promoters to decide what are the best estimates of a balance sheet from the community point of view. All this information must be organized and modulated through a multilevel model that leave women free to reach the depth and the breadth of information necessary to make a weighted decision, in a personalized way that should respect also the “right of not know”.

A personalized informative model could influence not only the participation in breast cancer screening, but also the awareness, the realistic expectations and the satisfaction of women about the decision process and their empowerment. The focus of the study is the informative process related to the decision about the participation in breast cancer screening within the national Health service screening programme. In this platform, benefits, harms and controversy of mammography screening will be fully presented.

3. STUDY OBJECTIVES

3.1 Primary

To assess the effect of an interactive web decision aid on informed choice – measured via knowledge, attitudes and intentions concerning breast cancer screening – comparing the decision aid with a standard information provided via web (web brochure).

3.2 Secondary

- To compare the participation rate in breast cancer screening between intervention (web decision aid) and control group (web brochure).
- To compare the satisfaction between the intervention (web decision aid) and the control group (web brochure) on information in terms of length, quantity, clarity, balance, helpfulness in making decision and women willingness to recommend it to other women.
- To measure the time spent on web pages between the intervention (web decision aid) and the control group (web brochure). Only for the intervention group, to measure number of pages visited, frequency of access, level of information and level of detail reached on the main topics.
- To compare the decisional conflict process between the intervention and the control group.

4. STUDY DESIGN

This is a multi-centre, randomised, controlled study to assess the efficacy of the high quality information approach driven by a multilevel web platform. The screening centres involved are based in different cities of Italy. In accordance with the target age of the women invited to the regional screening programmes, the present study will include 45-69 years or 50-69 years old new invited women. The eligible women will be invited to participate to the study through an ad-hoc letter by the belonging screening centre. The letter, delivered 30-45 days before of the standard screening program invitation letter, will provide information regarding the study and how to access to the web platform.

The women will be randomized to receive:

- Web platform with a multilevel information and an aid for the decision to be taken (whether participating or not to the mammography screening organised for free by the Italian Health Service). (Intervention group).
- Web platform with a standard brochure (Control group). This standard brochure represents a combination of the best information available from participant centre' brochures, see the

Appendix 1.

4.1 Intervention group: multilevel information and decision-aid

The content, in the web platform, is splitted in 16-20 screens (see Appendix 2); each screen contains the answer to a common question (i.e. What is mammography screening? What are its benefits and harms? What results can be expected from the participation to mammography screening? What is breast cancer?). The language is plain and the contents are defined on the basis of the literature. The information covers also controversial topics as overdiagnosis, overtreatment and the disagreement among scientists about harms and benefits' quantification.

Articles and review available in the literature, reports of Institutional organizations, such as ONS, GISMA, IARC, UK and USA guidelines, other screening materials (leaflets, website, brochure) are carefully considered in order to collect all the information needed to have a balanced and honest tool.

The content can be accessed through links that allow a more detailed comprehension of the topic (multilevel information).

The navigation is personalised; with a “nudging” approach the platform induces women to become aware of the relevant matters, nevertheless they can stop reading whenever they feel ready to decide. When women think of knowing enough and they are ready to decide (rational part) the platform provides a Decision Aid module where issues and concerns that can affect their decision are listed. Women are asked to say, for each items, the relevance and the impact on their decision (irrational part).

[figure not shown]
4.2 Randomization

A central system for randomization will be used inside the web platform. The women will be randomized after they register to the platform, sign the informed consent and fill-in the baseline questionnaire. The random allocation will be on a 1:1 ratio basis.

The overall duration of the study is 15 months: 14 months for invitation of the women and maximum 1 months of follow-up.

The study outline is illustrated in Figure 1.

Figure 1 Study flow-chart

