9.2 Statistical analysis

We will conduct a descriptive analyses to describe the study participants. Possible baseline differences between trial arms will be statistically tested.

For primary endpoint statistical analysis will be performed on an intention to treat approach: all the randomised women compliant to follow-up will be included in the analysis in the groups assigned at the randomization. The impact of the web decision aid on the primary endpoint will be analysed using Chi-square test.

For secondary endpoints we will use Chi-square test to analyse binary endpoints and 2-sided t-test for continuous endpoints, with a significance level of 5%.

We will use SAS statistical software, version 9.2.

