10.3 Data recording

Data collection will be performed using electronic CRFs exclusively.

The data will be registered in a MySQL database, to which only the site administrators (Zadig) will have access. The site administrators will insert users, who enter through centre lists. The system will give users an unambiguous ID, with which the data of each individual platform user will be associated. These data includes navigation, decisions, and questions. In this form, the data will be sent in CSV format. The data, subjected to statistical analysis, will be made anonymous, and provided in CSV format to the Mario Negri Institute. In general, the system permits tracing users in an unambiguous mode.

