It is only possible to estimate the reduction of mortality due to breast cancer by the mammography screening program, and of extra tumor diagnosis (overdiagnosis).

Participation in the screening provides the following benefits and harms to be assessed before taking a decision:

- Reduction of mortality due to breast cancer
- Overdiagnosis
- Less invasive treatments
- False positives or false negatives
- Radiation damage
- Inconvenience of the examination

What happens in the next 30 years?

What happens at 1000 women aged 50 in the next 30 years

Out of 1000 women aged 50 who regularly participate in a mammography screening program, in

the next 30 years:

- 71 will receive a diagnosis of breast cancer (discovered by screening or from clinical symptoms)
- 12 will die from breast cancer
- 8 will not die from breast cancer thanks to the screening
- 4 will receive overdiagnosis and useless treatments

If the same 1000 women are followed without a mammography screening program:

- 67 will receive a diagnosis of breast cancer
- 20 of them will die due to the breast cancer

In other words, in the next 30 years:

Some women will die from breast cancer anyway: 12 of the 1000 who participate in the mammography screening program compared to 20 if the screening program did not exist. Therefore 8 out of 1000 women are saved from death due to breast cancer; 4 of the 1000 women receive a diagnosis and are then treated uselessly for tumors detected by the screening that would probably never emerge. If there is no mammography screening program, there is no overdiagnosis and only evident tumors are treated.

At what age is mammography screening recommended?

In Italy the mammography screening program is carried out every two years for women aged 50-69 because there is impressive evidence of the reduction of mortality.

In some Italian regions (Emilia Romagna, Piedmont and Tuscany), the mammography screening program is extended to women aged from 45 to 49 every year and between 70 and 74 every two years. For these age bands the demonstration of the utility of screening is considered sufficient, though the balance of the related benefits and harms is still debated.

The European Code against Cancer (2015) confirmed the recommendation for women aged 50-69 to do the organized mammography screening and, in certain circumstances, also women aged 45-49 and 70-74.

The risks related to radiation

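### Centre is known before allocation but is not used in the analysis; a centre-stratified participation difference would gain 0 to about 4 points of power, depending on an unknown centre spread, at almost no cost

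*Combined protocol and SAP*

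**What the plan says.** **Allocation (4.2).** "A central system for randomization will be used inside the web platform", and "The women will be randomized after they register to the platform, sign the informed consent and fill-in the baseline questionnaire". The only further rule is "The random allocation will be on a 1:1 ratio basis". Strata, blocks and minimisation are not mentioned either way.

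**Analysis (9.2).** "The impact of the web decision aid on the primary endpoint will be analysed using Chi-square test". Binary secondary endpoints also get a chi-square test and continuous ones a two-sided t-test. No centre term appears.

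**Participation (5.2 and 9.1.3).** Participation is the first secondary endpoint. It is tested for non-inferiority only if the primary null hypothesis is rejected. Section 9.1.3 tabulates power for a single control rate of 40%, 408 women per arm and differences of 5, 10, 15 and 20 points. It calls the test one-sided but fixes neither a margin nor an alpha.

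**Centre.** The synopsis gives more than three centres, and section 4 places them in different cities. Age eligibility, 45-69 or 50-69, follows the local programme ("In accordance with the target age of the women invited to the regional screening programmes"), and the study letter comes from the woman's own centre. The decision-aid text in appendix 14.2 adds: "In some Italian regions (Emilia Romagna, Piedmont and Tuscany), the mammography screening program is extended to women aged from 45 to 49 every year". As general background, section 1.4 notes that "the several GISMA screening centers adopted different leaflets to invite the women to participate". On data entry, section 10.3 says: "The site administrators will insert users, who enter through centre lists".

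**The concern.** Participation is attendance at a local screening programme. Programmes in this trial can differ in target age and in how they invite women, so attendance may differ too. If it does, part of the variation in the outcome lies between centres. A pooled comparison leaves that variation in the standard error, and a centre-stratified one removes it. The platform already holds the information before a woman is allocated.

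What is at stake is power for the participation comparison. The plan's own table gives 0.83 at a 10-point difference and 0.29 at 5 points. There is also a practical link: a chi-square test of equality does not assess non-inferiority against a margin. That comparison needs an estimated difference with an interval, and centre can be taken into account in the same step.

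**Working it through.** **1. Reproduce the plan's figures.**
- Sample size (9.1.3): 50% against 60%, two-sided 5%, 80% power, continuity-corrected formula: 408 per arm, 816 in total. This matches.
- Invitations: 816 / (0.15 × 2/3) = 8160. This matches.
- Participation power: the plan gives no alpha. Take the tabulated difference Δ as the margin, a true difference of zero, 40% in both arms and one-sided 2.5%:

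  power = Φ(Δ / √(2 × 0.24 / 408) − 1.96), where 0.24 = 0.40 × 0.60 and the standard error is 3.43 points.

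| Δ | Plan | Recomputed |
|---|---|---|
| 5% | 0.291 | 0.308 |
| 10% | 0.828 | 0.830 |
| 15% | 0.993 | 0.992 |
| 20% | 1.000 | 1.000 |

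Agreement is within 2 points. One-sided 5% does not fit: it gives 0.426 and 0.898 for the first two rows.

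**2. Use centre.** A centre-stratified risk difference replaces 0.24 by the mean within-centre variance, V = mean of p(1 − p) over centres. The documents give no attendance by centre, so the spread is an assumption: three equal centres averaging 40%. For 30/40/50%, V = (0.21 + 0.24 + 0.25)/3 = 0.2333, and √(2 × 0.2333/408) = 3.38 points. At a 10-point margin:

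| Assumed attendance | V | SE (points) | Power | Gain (points) | Equivalent extra women |
|---|---|---|---|---|---|
| 40/40/40% | 0.2400 | 3.43 | 83.0% | 0 | 0 |
| 35/40/45% | 0.2383 | 3.42 | 83.3% | 0.3 | 6 |
| 30/40/50% | 0.2333 | 3.38 | 84.1% | 1.0 | 23 |
| 25/40/55% | 0.2250 | 3.32 | 85.3% | 2.3 | 54 |
| 20/40/60% | 0.2133 | 3.23 | 87.1% | 4.1 | 102 |

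The last column is 816 × (0.24/V − 1). The plan invites ten women per evaluable woman (8160/816), so 23 women correspond to about 230 invitations and 102 to about 1,020.

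**3. Other margins.** At 30/40/50% the gain is 0.7 points at a 5-point margin (30.8% to 31.5%) and 0.1 at 15 points. At 20/40/60% it is 3.2 and 0.4 points.

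**4. Chance imbalance between arms.** At 30/40/50% the between-centre variance is (0.01 + 0 + 0.01)/3 = 0.0067, which adds √(2 × 0.0067/408) = 0.57 points to the crude difference. Since 3.38² + 0.57² = 3.43², this is the same quantity as the loss in step 2 and already lies inside the crude standard error.

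**5. Simulation.** 40,000 trials per scenario, three equal centres, 816 women. The Monte Carlo error on power is √(0.83 × 0.17/40000), about 0.2 points.
- *Power at 30/40/50%:* 83.0% with simple allocation and crude analysis, 84.0% with simple allocation and stratified analysis, 84.2% with both stratified. At 20/40/60% the figures are 83.0%, 87.0% and 87.2%. Nearly all the gain comes from the analysis.
- *Type I error at the 10-point margin:* simple allocation with a crude test stays at 2.5% to 2.6% over the four spreads. Stratified analysis gives 2.4% to 2.7% under either allocation. Stratified allocation with a crude test falls to 2.1% at 25/40/55% and 1.9% at 20/40/60%.

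**6. Primary endpoint.** Informed choice of 45/50/55% or 40/50/60% across centres would give a variance reduction of 0.7% or 2.7%.

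**The case against.** The best reply is that no error is shown. A pooled chi-square after simple randomisation is valid, and the gain depends on a spread that the documents never give. This stands, and it limits the point to efficiency. The analysed women are also self-selected web registrants, about 10% of those invited (15% response, then one-third drop-out), so a gap between local programmes need not carry over to them. A zero gain is possible, and the top of the range needs a threefold difference in attendance between centres.

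Several stronger readings are tempting, and the documents do not support them:
- *That centre fixes the attendance level.* No section gives attendance by centre or says that it differs. The leaflet remark in 1.4 is background on screening centres generally, and within the trial all control women see one common brochure (section 4).
- *That chance imbalance is a second harm, able to push the estimate across a narrow margin.* It is the same variance counted again (step 4), and the plan fixes no margin, narrow or otherwise.
- *That the sponsor chose unstratified allocation.* Section 4.2 is silent on this.

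It is also fair to say that the missing margin and alpha matter more for this endpoint: tabulated power runs from 0.29 to 1.00 across the listed differences, a range that centre barely affects.

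What survives is that centre is recorded, is available before allocation, has documented links to age eligibility and the inviting programme, and is unused in the stated analysis.

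**Conclusion.** The point holds as a small, optional improvement. Leaving centre out of the participation analysis costs between 0 and about 4 points of power at a 10-point margin, and about 1 point at a spread of 30/40/50%. This rests on three equal centres averaging 40%, 408 women per arm and one-sided 2.5%. The centre spread is an assumption, the margin is one of four differences in the plan's table, and the alpha is inferred from that table. With more or unequal centres, what matters is the size-weighted variance of attendance between them.

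A reader might infer that the planned comparison is biased or that its type I error is inflated. Neither follows: under simple 1:1 allocation the crude test keeps its level. The effect on the primary endpoint is likely to be slight.

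**What to change.** **Section 9.2 (main change).** Estimate the participation difference as a Mantel-Haenszel risk difference stratified by centre, with a confidence interval, and base the non-inferiority comparison on that interval. Report the informed-choice difference in the same form. The sample size need not change.

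**Section 4.2 (optional).** State whether the platform stratifies by centre. If it does, for example with permuted blocks of random size, the analysis must be stratified as well, because stratified allocation with a crude test is conservative (about 1.9% instead of 2.5% at 20/40/60%). The converse does not apply: the stratified analysis works under simple allocation too.

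**Cost.** A few lines of SAS using centre, which is already recorded, and at most one setting in the randomisation module. Allocation is central and automated, so blocking by centre adds little predictability. No extra women or data items are needed.
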